8.3.2 DEFINITION OF SERIOUS ADVERSE EVENTS (SAE)

A serious adverse event is an adverse event that, in the opinion of the investigator or sponsor, results in: 1) death or is life-threatening (immediate risk of death); 2) hospitalization or prolongation of existing hospitalization; 3) persistent or significant incapacity or substantial disruption of the ability to conduct normal life functions (aka disability); or 4) congenital anomaly / birth defect.

8.3.3 CLASSIFICATION OF AN ADVERSE EVENT

8.3.3.1 Severity of Event

In general, grade categories are described as follows:

 – Grade 1 Mild; asymptomatic or mild symptoms; clinical or diagnostic observations only; no intervention indicated

- **Grade 2** Moderate; minimal, local, or noninvasive intervention indicated; limiting age-appropriate instrumental activities of daily life

- **Grade 3** Severe or medically significant but not immediately life threatening; hospitalization or prolongation of hospitalization indicated; disabling; limiting self-care ADL

- Grade 4 Life-threatening consequences; urgent intervention indicated.

- Grade 5 Death related to AE.

8.3.3.2 Relationship to Study Intervention

All adverse events (AEs) must have their relationship to study intervention assessed by the clinician who examines and evaluates the participant based on temporal relationship and his/her clinical judgment.

The degree of certainty about causality will be graded using the categories below. In a clinical trial, the study product must always be suspect

• Definitely Related – There is clear evidence to suggest a causal relationship, and other possible contributing factors can be ruled out. The clinical event, including an abnormal laboratory test result, occurs in a plausible time relationship to study intervention administration and cannot be explained by concurrent disease or other drugs or chemicals. The response to withdrawal of the study intervention (dechallenge) should be clinically plausible. The event must be pharmacologically or phenomenologically definitive, with use of a satisfactory rechallenge procedure if necessary.

• Probably Related – There is evidence to suggest a causal relationship, and the influence of other factors is unlikely. The clinical event, including an abnormal laboratory test result, occurs within a reasonable time after administration of the study intervention, is unlikely to be attributed to concurrent disease or other drugs or chemicals, and follows a clinically reasonable response on withdrawal (dechallenge). Rechallenge information is not required to fulfill this definition.

• Unlikely to be related – A clinical event, including an abnormal laboratory test result, whose temporal relationship to study intervention administration makes a causal relationship improbable (e.g., the event did not occur within a reasonable time after administration of the study intervention) and in which other drugs or chemicals or underlying disease provides plausible explanations (e.g., the participant's clinical condition, other concomitant treatments).

• Not Related – The AE is completely independent of study intervention administration, and/or evidence exists that the event is definitely related to another etiology. There must be an alternative, definitive etiology documented by the clinician.

8.3.3.3 Expectedness

Research physicians will be responsible for determining whether an adverse event (AE) is expected or unexpected. An AE will be considered unexpected if the nature, severity, or frequency of the event is not consistent with the risk information previously described for the study intervention

Expected RV AE		
Diarrhea	Nausea	Gas/Bloating
Expected COVID AE		
Fever	Fatigue	Dry Cough
Loss of appetite	Body Aches	Shortness of breath
Mucus/phlegm	Sore Throat	Headache
Chills	Loss of smell/taste	Stuffy nose
Nausea or Vomiting	Diarrhea	Stroke
Conjunctivitis	Lower extremity numbness,	"COVID Toes"
	swelling, pain	
Arrhythmias	Heart Attacks	Cardiomyopathy
Pulmonary Embolism	Death	

8.3.4 TIME PERIOD AND FREQUENCY FOR EVENT ASSESSMENT AND FOLLOW-UP

The occurrence of an adverse event (AE) or serious adverse event (SAE) may come to the attention of study personnel by way of participant online survey results and interviews of a study participant presenting for medical care, or upon review by a study monitor.

All AEs including local and systemic reactions not meeting the criteria for SAEs will be captured on the appropriate case report form (CRF). Information to be collected includes event description, time of onset, clinician's assessment of severity, relationship to study product (assessed only by those with the training and authority to make a diagnosis), and time of resolution/stabilization of the event. All AEs occurring while on study must be documented appropriately regardless of relationship. All AEs will be followed to adequate resolution.

Any medical condition that is present at the time that the participant is screened will be considered as baseline and not reported as an AE. However, if the study participant's condition deteriorates at any time during the study, it will be recorded as an AE.

Changes in the severity of an AE will be documented to allow an assessment of the duration of the event at each level of severity to be performed. AEs characterized as intermittent require documentation of onset and duration of each episode.

Research clinicians will record all reportable events with start dates occurring any time after informed consent is obtained until 7 (for non-serious AEs) or 30 days (for SAEs) after the last day of study participation. At each study visit, the investigator will inquire about the occurrence of AE/SAEs since the last visit. Events will be followed for outcome information until resolution or stabilization.

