1.2 SCHEMA

Prior to Enrollment Screening

•Total n=200

• Review electronic report of newly positive SARS-CoV2 test results of patients 45 and older

- •If old records are available, clinicians to prescreen for exclusion criteria
- •Contact potenially eligible participants by phone to discuss interest in study
- •Patient referred to an online site to review a video discribing the study, risk, benefits.
- Patient given the opportunity to ask questions
- •Obtain informed consent electronically
- •Screen potential participants by inclusion and exclusion criteria
- •Obtain history, document

Randomization

•Intervention Group 1 (n=100)

•Placebo (n=100)

Day1

Baseline Survey & Start treatment

•Patient take Vitamin D3 100,000 IU on day and starts treatment or placebo

• Patients will receive an baseline assessment using Patient-Reported Outcomes version of the Common Terminology Criteria for Adverse Events (PRO-CTCAE[™]).

Day 2-15

Treatment or placebo and daily online survey

•Participant to take 2 capsules of intervention or placebo 4 times per day for 15 days.

• Participant will receive a daily online survey to assess for signs and symptoms of COVID-19 and to report potential side effects. If a patient has not completed an online survey within 24 hours, the patient will be contacted via phone to check their status.

Day 8, 15, 21

Weekly PRO-CTCAE Survey

•Patients will questionnaire with 7 day look back of adverse events based on the Patient-Reported Outcomes version of the Common Terminology Criteria for Adverse Events (PRO-CTCAE[™]).

Between day 21-30 Follow-up assessments for efficacy

•Clinicians will perform a chart review to assess patient outcomes as well as contact patient for an exit interview via phone.

Day 30 and Day 60

Long term assesment

[figure not shown]
• Participant Completes PRO-CTCAE to evaluate for adverse events

Study Completion Follow-up assessments of study endpoints and safety

•Data analysis

• Possible long term follow up of adverse events as outlined in section 8.3

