Participant Monitoring and Follow-up: Starting on day 1, and continuing daily for 15 days, subjects will be contacted via e-mail or text message (according to the subject's preference. Messages will include a reminder to take their study medication as scheduled and complete the daily survey (see appendix 12.6.1) each evening prior to going to bed. Subjects will be asked to complete a short questionnaire covering: 1) symptoms they had that day that may be related to COVID-19 (e.g., fever, cough, dyspnea), their frequency and severity; 2) report any other related or non-related medical events; 3) any medications they have taken to relieve symptoms, or other new medications they have not previously reported to study personnel; and 4) any visits they have made to healthcare providers, outpatient centers or hospitals, and details regarding those visits. Subjects will be reminded to contact their primary care physician if they experience symptoms that are worsening or that are concerning to them. For any such contact, they should inform their physician or other healthcare provider that they are enrolled in a clinical trial involving a dietary supplement.

Participants with complete on online PRO-CTCAE questionnaire on days 1, 8 (+1 day), 15 (+1 day), 21 (+1 day), 30, and 60 to monitor for adverse events.

Subjects who do not complete questionnaires will receive a reminder Xe-mails. All patients will be called for a phone interview after 21 days. If subjects cannot be contacted via phone, study personnel will attempt to contact the spouse/family member/friend who is listed as the secondary contact in order to determine the subject's status. A subject will be considered lost to follow-up if their status concerning hospitalization during the study period cannot be verified.

Outcome Assessment and Other Key Variables. Hospitalizations will be determined based on query of subject and/or the subject's secondary contact. The subject's medical records will be requested from the admitting hospital (and discharging hospital, if separate) via a HIPAA authorization.

Additional outcomes will include assessing number of days with fever and to assess symptoms, including dyspnea and fatigue. Questionnaires to assess symptoms will be based on the PRO-CTCAE (see appendix 12.6) (National Cancer Institute, 2020).

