4.4 END OF STUDY DEFINITION

A participant is considered to have completed the study after they have completed a minimum of 7 days of treatment, noting patient will be permitted to discontinue treatment after having 3 days of resolution of fever, fatigure, and dyspnea and they has been followed up with 60 days of enrollment by way of completing the last online survey, exit interview and/or chart review.

The study is considered complete after the last enrolled participant has completed the study.

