12.4 SAMPLE PATIENT PACKET ITEMS

12.4.1 SAMPLE DRUG DIARY

Front Page

Back Page

SYMPTOMS/SIDE EFFECTS

Please record any side effects experienced during this cycle. Include the date the particular symptom started and when it ended. Please evaluate the severity of the symptom according to the following scale:

Mild: Awareness of sign or symptom; easily tolerated and did not affect ability to perform normal daily activities. Symptom did not require medication or therapeutic intervention.

Moderate: Significant discomfort which interfered with ability to perform normal daily activities. Symptom was easily resolved with at home medication or simple therapeutic intervention.

[figure not shown]
Severe: Marked discomfort with an inability to carry out normal daily activities. Symptom required new medication and/or therapeutic intervention in order to resolve.

Please Note: The severity should reflect the most severe level experienced during the time period.

We will ask you to report your symptoms and side effects on day 1, 8, and 15 via an online questionaire.

	Symptom	Start Date	End Date	Severity
ł				
ľ				
Ì				
ľ				
Ì				
Ì				
ł				
ł				

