Runny nose (rhinorrhea)	0	0	0
Sore throat	0	0	0
Cough (new onset or worsening of chronic cough)	0	0	0
Shortness of breath (dyspnea)	0	0	0
Nausea or Vomiting	0	0	0
Headache	0	0	0
Abdominal pain	0	0	0
Diarrhea (>3 loose/looser than normal stools/24hr period)	0	0	0

What's your highest temperature within the past 24 hours? (If you have access to a thermometer)

(Farenheight temperature)

06-19-2020 10:50

Page 2 of 3

Overall how do you feel compared to yesterday?	Much worse	Same	Much better	
			lace a mark on the scale above)	
TODAY, what was the SEVERITY of your SHORTNESS OF BREATH, at its WORST	 None Mild Moderate Severe, Very Severe 			
TODAY, how much did your SHORTNESS OF BREATH INTERFERE with your usual or daily activities	 Not at all A little bit Somewhat Quite a bit Very much 			
TODAY, what was the SEVERITY of your FATIGUE, TIREDNESS, OR LACK OF ENERGY at its WORST?	 None Mild Moderate Severe, Very Severe 			
TODAY, how much did FATIGUE, TIREDNESS, OR LACK OF ENERGY INTERFERE with your usual or daily activities?	 Not at all A little bit Somewhat Quite a bit Very much 			
TODAY, how OFTEN did you have LOOSE OR WATERY STOOLS (DIARRHEA/DIARRHOEA)?	 Never Rarely Occasionally Frequently Almost constantl 	У		
Other symptoms - 1	0		M	
Other symptoms - 1, specify:			2	
Other symptoms - 2	0			
Other symptoms - 2, specify:				
Other symptoms - 3	0	کہ		
Other symptoms - 3, specify:				
Have you had to seek medical attention in the past 24 nours?	Yes, called a help Yes, when to an Yes, I was admitt None of the aboy	urgent care / er ed to the hospi	nergency departmer tal	
Other:				
	.	3		

06-19-2020 10:50

projectredcap.org

NIH-FDA Clinical Trial Protocol Template – v1.0 2017-04-07

Page 3 of 3

Have you have any other medical events within the past 24 hours (not previously reported)? This could include items not necessarily related to COVID-19, such as a car accident, broken bone, or new/worsening of another medical condition.

National Center for Immunization and Respiratory Diseases (NCIRD), Division of Viral Diseases

06-19-2020 10:50

projectredcap.org **REDCap** 84 | Page

6.2 – PRO-CTCA		(1, 8, & 15, 21, 30, AND 60)	
fidential	These are DRAFT exampl will be finalized before p	atient enrollment Resveratroi for COVID-	
PRO-CTCAE	CTCAE Note that questions will be formatted for		
	electronic viewing and w	ill have conditional	
Study ID	formatting such that only relevant questions will		

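### Adverse events are to be recorded to about day 67 and SAEs to about day 90, but in the readable text days 31 to 53 and everything after day 60 are not systematically solicited

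*Combined protocol and SAP*

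**What the plan says.** - **Recording window.** Section 8.3.4 runs from consent "until 7 (for non-serious AEs) or 30 days (for SAEs) after the last day of study participation". The synopsis gives a participant duration of 60 days. Section 4.4 counts a participant as complete once "followed up with 60 days of enrollment by way of completing the last online survey, exit interview and/or chart review" has taken place, alongside a minimum treatment period.
- **Adverse event questionnaire.** Section 4.1 schedules the PRO-CTCAE "on days 1, 8 (+1 day), 15 (+1 day), 21 (+1 day), 30, and 60 to monitor for adverse events". For the day 8, 15 and 21 surveys the schema describes a "questionnaire with 7 day look back of adverse events". The form in Appendix 12.6.2, headed for all six days, carries the same 7-day recall in its timed items. Its items are symptoms plus free-text entries for other symptoms.
- **Admission and care sought.** The question beginning "Have you had to seek medical attention in the past 24" (hours), and a further question on other medical events, stand in the daily questionnaire of Appendix 12.6.1. Section 4.1 runs that survey for 15 days from day 1.
- **Interview and chart review.** The schema places both between days 21 and 30. For days 30 and 60 it lists completion of the PRO-CTCAE only.
- **Finding hospitalizations.** Sections 4.1 and 8.1 rely on asking the participant or the secondary contact, then requesting records from the admitting hospital.
- **What participants are told.** The sample diary sheet in Appendix 12.4.1 reads: "We will ask you to report your symptoms and side effects on day 1, 8, and 15 via an online questionaire".

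**The concern.** The period over which events are to be recorded is longer than the period over which anyone is described as asking about them. Evaluating safety is a stated aim (section 4.1), and the expected COVID-19 events in section 8.3.3.3 include stroke, pulmonary embolism, heart attack and death. An admission on day 40 is an SAE inside the 8.3.4 window. Yet the next listed contact is a day-60 form that looks back to about day 54 and asks about symptoms, not admissions. An admission on day 75 is also inside the window, with no listed contact at all.

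Section 9.4.4 also promises a start date, stop date and duration for each event. The readable PRO-CTCAE form has no date fields. The diary sheet has date columns, but its text is tied to a treatment cycle and to questionnaires on days 1, 8 and 15. What is at stake is whether event counts for the later part of follow-up rest on active enquiry or on whatever happens to come to light.

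**Working it through.** The plan states no figure for this point, so there is none to reproduce. The check is a count of calendar days.

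**Inputs**
- Last day of participation: day 60 (synopsis; section 4.4).
- Recording extends 7 days beyond this for non-serious events and 30 days for SAEs (section 8.3.4).
- PRO-CTCAE on days 1, 8, 15, 21, 30 and 60 (section 4.1), recall 7 days (schema; Appendix 12.6.2).
- Daily survey on days 1 to 15 (section 4.1).
- Exit interview and chart review between days 21 and 30 (schema).

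**Step 1: end of each window.** Non-serious events: 60 + 7 = day 67. SAEs: 60 + 30 = day 90.

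**Step 2: days covered by each form.** A form on day d with 7-day recall covers days d − 6 to d.

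| Form | Days covered |
|---|---|
| Day 21 | 15–21 |
| Day 30 | 24–30 |
| Day 60 | 54–60 |

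The daily survey covers days 1 to 15.

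**Step 3: days not covered.**
- Days 22–23: the interview or chart review can cover these if held late enough in its window, so they are not counted as a gap.
- Days 31–53: 53 − 31 + 1 = 23 days, which is 23 / 30 = 77% of days 31 to 60.
- Days 61–67 (non-serious events): 7 of 7 days.
- Days 61–90 (SAEs): 30 of 30 days.

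From day 31 to the end of the window, the unprompted days are 23 + 7 = 30 of 37 (81%) for non-serious events and 23 + 30 = 53 of 60 (88%) for SAEs.

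**Step 4: sensitivity to how recall is counted.** If a form on day d covers d − 7 to d − 1, the day-30 form covers days 23–29 and the day-60 form days 53–59. The main gap becomes days 30–52, again 23 days, and day 60 itself falls outside recall.

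**Step 5: content of the forms.** Even inside days 24–30 and 54–60, the PRO-CTCAE asks about symptoms. The questionnaire items on admission or care sought and on other medical events are in the daily survey, which ends at day 15. The last described occasion on which a participant would be asked about hospitalization is therefore the interview after day 21.

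**The case against.** A reader might infer that events on days 31–53 and after day 60 go uncollected, or that the plan has no means of finding them. The documents do not support that:
- Section 4.4 lets chart review complete the 60-day follow-up, and chart review has no 7-day recall limit.
- Section 8.3.4 has the investigator ask at each study visit about events since the previous one. It also names presentation for care and monitor review as routes.
- The schema says long-term follow-up of adverse events is possible.
- A sentence in section 4.1, broken in the readable text, concerns outpatient visits and hospitalizations over the 60 days.
- Only the heading of the Schedule of Activities can be read, so a day-60 call or chart review cannot be excluded.

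These points limit the finding without removing it. In 4.4 the routes are alternatives, so returning the last survey is enough. No visit is described after day 30. Permission to obtain records does not by itself reveal an admission.

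Other tempting extensions also fail:
- Capture is not confined to the sponsor's own health system. Section 7.3 reaches secondary contacts, two other hospital systems and vital records, although only when a participant's outcome cannot otherwise be determined.
- Pregnancy is not among the SAE criteria of 8.3.2; sections 8.3.5 and 8.3.9 handle it separately.
- The diary sheet does not say that days 1, 8 and 15 are the only questionnaire days.
- The opening free-text question on the PRO-CTCAE has no recall period in its wording, though the severity items that follow do.
- Section 9.4.4 does not claim complete 60-day ascertainment.

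It is also fair to say that 8.3.4 defines which events are recorded, not how they are sought; a recording window longer than the contact schedule is a mismatch rather than a contradiction. Dosing ends on day 15, the plan quotes half-lives of about 5 to 8 hours, the efficacy endpoints close at day 21, and the gap applies to both blinded arms. Both questionnaires are marked as drafts. These points lower the stakes, and the draft status makes the change easy. They do not supply the missing question.

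**Conclusion.** The point holds as a mismatch between the recording window and the described means of finding events. In the readable text, 23 of the 30 days from day 31 to day 60, all 7 later days for non-serious events and all 30 later days for SAEs are not systematically solicited. The day-60 form has no question on admission or care sought. Capture in these periods would depend on chart review where it is done, on spontaneous report, or on chance.

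This assumes that the last day of participation is day 60 and that the draft forms are used as shown. It also assumes that the unreadable Schedule of Activities adds no contact or record check after day 30. If that table contains a day-60 call or chart review, the gap in days 31–53 narrows or closes. The text describes no contact after day 60. Efficacy analyses are unaffected. Separately, the diary sheet (days 1, 8, 15) and the questionnaire schedule (days 1, 8, 15, 21, 30, 60) differ and need reconciling. The sponsor should make the change, but it is not a reason to hold the trial.

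**What to change.** 1. Leave the PRO-CTCAE items at 7-day recall. Add the two existing daily-survey questions (medical attention or admission; other medical events) to the day 21, 30 and 60 forms, worded *since your last survey*.
2. State that the calls to survey non-responders (section 5.5) and to the secondary contact (section 4.1) also apply when the day-60 form is not returned.
3. Reconcile the 8.3.4 window with the last scheduled contact, either by ending it there or by scheduling one contact at its end. If the Schedule of Activities already contains a day-60 check, say so in 8.3.4 and the schema.
4. Reconcile the diary sheet with the questionnaire schedule.

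The cost is two existing questions on three draft forms, a wording change in 8.3.4, a corrected diary sheet and about a minute of participant time per form. If a closing contact is chosen in step 3, that adds one contact per participant, at most 200.

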8.3.5 ADVERSE EVENT REPORTING

All adverse events (AEs) will be recorded in the Case Report Form (CRF), and will be reviewed on an ongoing basis by the investigator and DSMB. The Principal Investigator shall be solely responsible for complying, within the required timelines, with any safety reporting obligation to competent Health Authorities and the IRB, as defined in applicable laws and regulations. For the purposes of this section, safety data includes adverse events, product quality complaints (PQCs), and special situations including pregnancies.

